6.8 Determination of Sample Size and Accrual Rate

Although this is a feasibility study, we will provide a sample size estimate based on the difference in sensitivities between ^{68}Ga -PSMA PET and either ^{131}I and ^{18}F -FDG. To provide an estimate of the needed sample size we assumed that half of the patients will be imaged with ^{131}I and half the patients will be imaged using ^{18}F -FDG PET within 360 days of the ^{68}Ga -PSMA-11 imaging study. We will compare the sensitivity of both ^{131}I and ^{18}F -FDG to ^{68}Ga -PSMA PET. Assuming that both ^{131}I and ^{18}F -FDG have a sensitivity of 0.65 and ^{68}Ga -PSMA PET has a sensitivity of 0.90. Our null hypothesis is that there is no difference between either ^{131}I and ^{18}F -FDG and ^{68}Ga -PSMA PET misclassification rates (H_{null} : ^{131}I / ^{18}F -FDG_misclass = PSMA PET misclass = 65%). The alternative hypothesis is that the FET PET misclassification rate is lower (H_{alt} : PSMA PET misclass < ^{131}I / ^{18}F -FDG_misclass = 65%). Given a power of 0.87, a significance level of 0.05, and a one-sided test, we will require 20 patients for comparison to ^{18}F -FDG and 20 patients for comparison to ^{131}I . This will result in a total sample size of 40. The anticipated accrual rate is approximately 1 to 2 patients per month, leading to an estimated total accrual period of up to 18 to 24 months.

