6.10 Analyses Plans

The number of ^{68}Ga PSMA-11 PET-positive lesions and number of overall thyroid cancer lesions detected by standard staging scans will be descriptively reported for each patient and correlated with the lesions observed in standard MRI imaging. In addition, the mean, range, and standard deviation of SUV_{max} (across all visualized lesions per patient) and $SUV_{max-avg}$ (across all patients in the study cohort) will be descriptively reported.

For each lesion detected on ^{18}F -FDG PET or radioiodine scintigraphy (^{131}I), the presence or absence of ^{68}Ga -PSMA-11 uptake will be reviewed and tabulated. Presence on either ^{131}I and ^{18}F -FDG will be considered true positive disease. If additional lesions are detected on ^{68}Ga -PSMA-11 as compared to ^{18}F -FDG or ^{131}I , the lesions will be characterized as either true or false positives in comparison to the appearance of the lesion on conventional imaging (thyroid ultrasound, CT and MRI). The gold standard for an individual lesion will be FDG or ^{131}I , if the individual lesion is positive on either imaging study. If the lesions are not seen on either FDG or ^{131}I , then consensus reading of conventional imaging will be performed to determine true and

false positive lesions. The total number of lesions detected using each technique will be compared, and this data will be used to determine the sensitivity and specificity of ^{68}Ga -PSMA-11 for the detection of disease. If a larger number of lesions are detected using ^{68}Ga -PSMA-11 compared to ^{18}F -FDG PET and ^{131}I , this provides promising preliminary data, which can be used to justify study in a larger clinical trial.

The patient cohort will be dichotomized by thyroglobulin level. The mean $\text{SUV}_{\text{max-avg}}$ between dichotomized subgroups will be compared using the non-parametric Mann-Whitney U test. The correlation between SUV_{max} on ^{68}Ga -PSMA PET and thyroglobulin level as a continuous variable will also be determined using Pearson correlation method.

In those patients with adequate archival FFPE the correlation between SUV_{max} on ^{68}Ga -PSMA PET and tumor PSMA expression will be explored using Pearson correlation method.

7 Study Management

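### Section 6.10 lets any excess of lesions on PSMA PET count as promising, with no margin, interval or test, although 6.8 sizes that comparison at a one-sided 0.05 level; the false-positive rate is uncontrolled.

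*Combined protocol and SAP*

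**What the plan says.** Section 6.8 gives the design of the comparison: "Given a power of 0.87, a significance level of 0.05, and a one-sided test", "we will require 20 patients for comparison to" each of FDG and I-131, 40 in all. The assumed sensitivities are 0.65 for both comparators and 0.90 for PSMA PET.

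Section 6.10 names tests for the thyroglobulin question (Mann-Whitney, Pearson) and for tissue PSMA expression (Pearson). It names none for PSMA against FDG or radioiodine. There it says that lesion totals by technique will be compared and will feed estimates of sensitivity and specificity. It then gives one forward-looking criterion, which opens "If a larger number of lesions are detected using" PSMA-11 than with FDG PET and I-131, and ends "this provides promising preliminary data, which can be used to justify study in a larger clinical trial". No margin, interval, significance level or unit of analysis is attached.

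Three other provisions bear on the count:
- Inclusion criterion 2 (3.3.1) admits only patients whose FDG or radioiodine scan already shows uptake.
- Section 6.7 limits analysis to five lesions per study.
- Under 6.10 a lesion on FDG or I-131 is true disease by definition, while a PSMA-only lesion is judged by consensus reading of conventional imaging.

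**The concern.** The plan sets a 5% error level when it justifies the sample size, then offers a criterion with no allowance for sampling error when it says what result would be encouraging. Two scans of equal sensitivity will rarely find exactly the same number of lesions, so one of them leads by chance in most trials. If PSMA leads by a single lesion, the sentence in 6.10 is satisfied.

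This is the only stated route from the comparative result to a larger trial. A reader of the final report could take a favourable statement as carrying the 0.05 level in 6.8, and it would not.

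**Working it through.** **Inputs from the documents.** Sensitivity 0.65 for each comparator, 0.90 for PSMA under the alternative, one-sided 0.05, power 0.87, 20 patients per comparison and 40 in total (6.8); positive qualifying scan (3.3.1); at most five lesions (6.7).

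**Inputs assumed, because the documents do not give them.** Lesions per patient: fixed at 1 to 5, or a mean of 2 to 5 capped at five. Within-patient correlation: 0 to 0.3. Agreement between scans: independent given the lesion, so discordance is 2 × 0.65 × 0.35 = 0.455; lower values were also tried.

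**1. The plan's own power.** Treat 0.65 as a fixed reference and require at least 17 detections in 20. Then P(X ≥ 17 | 0.65) = 0.044 and P(X ≥ 17 | 0.90) = 0.867. This reproduces 0.87, so the stated power belongs to a formal test at 0.05, not to a comparison of totals.

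**2. Equal sensitivity, no selection, all counted lesions true.** Each lesion contributes +1, 0 or -1 to the PSMA lead, with +1 and -1 equally likely. By symmetry, P(PSMA larger) = (1 - P(tie)) / 2. With 40 patients pooled:
- 40 lesions: (1 - 0.0933)/2 = 0.453
- 80 lesions: (1 - 0.0660)/2 = 0.467
- 120 lesions: (1 - 0.0539)/2 = 0.473
- 200 lesions: (1 - 0.0418)/2 = 0.479

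If the scans agree more closely (discordance 0.10), the range is 0.398-0.455. Simulation with mean 2-5 lesions and correlation 0-0.3 gives about 45-49%.

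**3. Add inclusion criterion 2.** If the qualifying scan is the comparator, every patient has at least one comparator-positive lesion. With k independent lesions the expected comparator count becomes 0.65k / (1 - 0.35^k), while PSMA stays at 0.65k. For k = 2 this is 1.3/0.8775 = 1.48 against 1.30, a comparator head start of about 7.3 lesions over 40 patients. For k = 3 it is 2.04 against 1.95 (about 3.5 lesions); for k = 5, 3.27 against 3.25 (about 0.7). Simulated P(PSMA larger), with the correlation in brackets:

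| Lesions per patient | 20 patients (0) | 20 patients (0.3) | 40 pooled (0) | 40 pooled (0.3) |
|---|---|---|---|---|
| 1 | 0.00 | 0.00 | 0.00 | 0.00 |
| 2 | 0.13 | 0.05 | 0.07 | 0.01 |
| 3 | 0.32 | 0.16 | 0.28 | 0.08 |
| 4 | 0.41 | 0.22 | 0.41 | 0.16 |
| 5 | 0.45 | 0.30 | 0.45 | 0.22 |

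Letting the number vary between patients (mean 2-5, capped at five) gives about 7-40% with 20 patients and 3-40% with 40.

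**4. PSMA must exceed both comparators, in separate cohorts of 20.** Square the single-cohort rate. Without selection this runs from 0.434² = 0.19 to 0.470² = 0.22. With selection it is 0.00-0.20.

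**5. Confirmation.** If conventional imaging confirms only 90% of PSMA-only lesions, the unselected rate falls to about 0.30-0.37. If unconfirmed foci count, since 6.10 speaks of lesions detected, an assumed 0.1 false foci per patient gives 0.00-0.62 under selection.

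**6. The lead that 5% would require.** With independent lesions, discordance 0.455 and no selection, PSMA would have to lead by at least 8 of 40 lesions (size 0.039), 11 of 80 (0.041), 13 of 120 (0.045) or 17 of 200 (0.042), rather than by 1. Clustering within patients would widen these margins.

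**The case against.** A reader might infer that 6.10 contains a go-forward rule that is met in almost half of trials when PSMA is no better, against a promised 5%. The documents do not support that reading, for four reasons.

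- **Selection.** Inclusion criterion 2 tilts the count towards the qualifying scan. Under it the rate runs from near zero to about 45%, depending on quantities the documents do not give, and some settings with 40 patients fall below 5%.
- **Wording of the comparison.** Section 6.10 names FDG PET and I-131 together. Read as requiring both, the rate is about 20% or less.
- **The 5%.** The 0.05 in 6.8 belongs to a comparison of sensitivity. Section 6.10 does not attach it to the lesion count.
- **Force of the sentence.** The data can be used to justify a larger trial. That is permissive language in a single-centre feasibility study and triggers no action.

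All four stand, and they rule out a single headline rate. They do not supply an error bound. Selection also protects only the scan that qualified the patient: a radioiodine comparison in someone who qualified on FDG is not protected. Counting unconfirmed foci pushes the rate the other way. A rate that can move from 0 to above 0.5 on unstated quantities is uncontrolled.

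**Conclusion.** The point holds in a limited form. Section 6.8 sizes the comparison at a one-sided 0.05 level, 6.10 applies no test to it, and an excess of one lesion qualifies as promising.

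The size of the problem depends on the selection and on the reading of the sentence: about 45-49% of trials without selection on the comparator, about 7-40% (20 patients) or 3-40% (40 pooled) with it, and about 20% or less if both comparators must be exceeded in separate cohorts. These figures assume equal sensitivity 0.65, a mean of 2-5 lesions capped at five, correlation 0-0.3, scans independent given the lesion, and all counted lesions true. With exactly one lesion per patient and a guaranteed positive comparator scan, PSMA cannot lead at all.

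This weakens what the study may claim from its comparison. It does not affect its descriptive results.

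**What to change.** In 6.10, replace the sentence on a larger number of lesions with the following.

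- For each patient who had both scans, compute confirmed lesions on PSMA minus those on the comparator, separately for FDG and for radioiodine.
- Report the mean paired difference with a one-sided 95% lower bound, using the patient as the unit (sign-flip test or bootstrap).
- Call a comparison promising only if that bound exceeds 0.

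If the sponsor does not want such a test, label the counts descriptive and delete the go-forward statement.

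The work is a paragraph of text and a few lines of code. Three costs should be stated in the plan:

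- **Conservatism and power.** Because patients are selected on a positive comparator scan, the size is about 0-4%. At 0.90 against 0.65, power with 20 patients is about 31-99% for a paired t version, depending on lesions per patient and clustering. A sign-flip version can be lower: 20% with a mean of two lesions and correlation 0.3.
- **Selection bias.** The bound does not remove it; name it as a limitation.
- **Two comparisons.** Each is tested at 5%, so the chance of at least one false positive is higher than 5% unless this is adjusted for or stated.

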2.2 Secondary

1. To assess the correlation between targeted molecular uptake of ⁶⁸Ga-PSMA PET in thyroid cancer compared to areas identified as tumor by radioiodine uptake (in well-differentiated cancers) or ¹⁸F-FDG uptake (in poorly differentiated and/or radioiodine-negative cancers).
2. To determine and compare the sensitivity and specificity of ⁶⁸Ga-PSMA PET to ¹⁸F-FDG PET and/or radioiodine scintigraphy

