2.3 Exploratory Objectives, Other Assessments

1. To determine if ⁶⁸Ga-PSMA PET uptake is related to tumor differentiation and PSMA staining in tissue pathology when available
2. To determine the correlation between SUV_{max} of target thyroid cancer lesions on ⁶⁸Ga-PSMA PET and serum thyroglobulin levels.

3 Study Design

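### The thyroglobulin analyses pool radioiodine-imaged and FDG-imaged patients without adjustment, so the exploratory association can reflect cohort mix or hide a within-group relation

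*Combined protocol and SAP*

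**What the plan says.** Exploratory objective 2 (section 2.3) asks for the correlation between thyroglobulin and the SUVmax "of target thyroid cancer lesions on" PSMA PET. Section 6.10 answers it in two ways. First, "The patient cohort will be dichotomized by thyroglobulin level", and mean SUVmax-avg "between dichotomized subgroups will be compared using the non-parametric Mann-Whitney U test". No cut-point is given. Second, the association of SUVmax with "thyroglobulin level as a continuous variable will also be determined using Pearson correlation method". Neither analysis names a stratum, a covariate or separate reporting by scan type, histology or differentiation, and no other section supplies one.

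Elsewhere the protocol does distinguish patients on these lines. Secondary objective 1 (section 2.2) takes as its reference "radioiodine uptake (in well-differentiated cancers") and FDG uptake for poorly differentiated or radioiodine-negative disease. The sample-size section (6.8) assumes that "half of the patients will be imaged with" I-131 and half with FDG, giving 20 patients for each comparison. Exploratory objective 1 asks whether PSMA "PET uptake is related to tumor differentiation and PSMA staining in tissue pathology when available".

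**The concern.** The protocol treats differentiation as a possible driver of PSMA uptake and separates patients by a marker of it. It then ignores that marker when it relates uptake to thyroglobulin. If thyroglobulin also differs between the groups, a pooled correlation combines two things: the relation among similar patients, and the distance between the two group averages. The second part can produce an association where no relation exists within either group, or cancel one that does. It also changes with the enrolment mix, so the same biology could give a different answer in a later study. At stake is the reading of exploratory objective 2, for which these are the only planned analyses.

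**Working it through.** **The plan's own figure.** The only sample-size figure is a power of 0.87 with 20 patients per comparison (section 6.8: sensitivity 0.65 against 0.90, one-sided 0.05). An exact one-sample binomial test with n = 20 and success at 17 or more gives alpha 0.044 and power 0.867, which reproduces it. That figure belongs to the sensitivity comparison and neither supports nor refutes this point. No figure is given for the thyroglobulin analyses.

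**Inputs.** From the documents: N = 40 and an expected 20/20 mix. Assumed, because the documents give nothing: the between-group shifts dx (thyroglobulin) and dy (SUV) in within-group SDs, the within-group correlation ρ, and a median split for the Mann-Whitney test.

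**Pooled correlation of a two-group mixture**, with share p in one group:

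r = [ρ + p(1−p)·dx·dy] / √{[1 + p(1−p)dx²]·[1 + p(1−p)dy²]}

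At p = 0.5, p(1−p) = 0.25. With ρ = 0 and equal shifts d in the same direction:

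- d = 0.5: 0.0625/1.0625 = 0.06
- d = 1: 0.25/1.25 = 0.20
- d = 1.5: 0.5625/1.5625 = 0.36
- d = 2: 1/2 = 0.50

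Opposite shifts give the same values with a minus sign. If only one variable shifts, dx·dy = 0 and r = 0.

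**Rejection rates by simulation** (3,000 to 4,000 trials, N = 40, 20/20, ρ = 0, two-sided 0.05):

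| Shift in both (SD) | Mann-Whitney, median split | Pearson, log values | Pearson, raw values (opposite shifts) | Group-adjusted correlation |
|---|---|---|---|---|
| 0.5 | 6% | 6% | about 4% | 5% |
| 1 | 19% | 25% | 3-8% | 5% |
| 1.5 | 58% | 68% | 5-26% | 5% |
| 2 | 92% | 96% | 10-52% | 5% |

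The raw-value column assumes a within-group log-SD of 0.6 for SUV and 1 to 2 for thyroglobulin; more skew gives lower rates. It is the column closest to the Pearson analysis in section 6.10, which mentions no log transformation. Taking logs does not change the Mann-Whitney result. A shift of 1 SD in one variable only gives about 5% for both the Mann-Whitney test and Pearson on log values.

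**Hidden relation**, true ρ = 0.5, opposite shifts:

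- 1 SD: r = (0.5 − 0.25)/1.25 = 0.20. Pearson on log values detects it in about 21% of trials.
- 1.5 SD: r = (0.5 − 0.5625)/1.5625 = −0.04. Pearson on log values detects it in about 4%.

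A group-adjusted Pearson correlation detects it in about 92% in both cases, and a group-adjusted rank correlation in about 87%. At 1.5 SD the van Elteren test detects it in about 59%. Under ρ = 0 the rank correlation and the van Elteren test both stay near 5%.

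**Effect of mix alone**, ρ = 0, shifts of 1 SD in the same direction: r = 0.20 at 20/20; 0.1875/1.1875 = 0.16 at 30/10; 0.09/1.09 = 0.08 at 36/4.

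**The case against.** The strongest reply is that objective 2 asks for a correlation in the study population. A pooled r is a true marginal association there, so the rejection rates above are not false positives for that question. This stands: the pooled result misleads only if it is read as a relation among comparable patients.

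It also stands that the mechanism needs both variables to shift. Differentiation as a driver of PSMA uptake is an open question in section 2.3. On thyroglobulin, the background (section 1.1) mentions elevation with negative iodine scans, and the abstract expects elevation in all patients. Neither says how the groups differ.

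A reader might infer more than the documents support:

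- *That thyroglobulin falls as tumours lose differentiation, or that radioiodine patients are TSH-stimulated when sampled.* The documents say neither. Thyroglobulin is a screening test within 28 days of Day 1, while the qualifying scan may be up to 360 days old (sections 5.1.1 and 3.3.1), so nothing ties the sample to a radioiodine scan. For the same reason there is no basis here for excluding antibody-positive patients.
- *That the planned Pearson test would reject in 25% to 96% of trials.* Those rates are for log values with shifts of 1 to 2 SD; the raw-scale rates are lower.
- *That the trial has two fixed cohorts of 20.* The even split is a planning assumption. Eligibility sets no quota, and a patient may have both scans.

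Finally, no stopping rule, sample size or go-forward statement uses this analysis.

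**Conclusion.** The point holds in conditional form. Section 6.10 pools patients whom the protocol itself separates by scan type and differentiation, and the pooled association cannot be told apart from a difference between the groups. The effect is negligible at shifts of 0.5 SD or less and absent if only one variable shifts. It becomes material for the Mann-Whitney test from about 1 SD in both variables (about 19%), and for the raw-scale Pearson mainly at 1.5 to 2 SD (5-26% and 10-52% for opposite shifts, depending on skew). Masking is possible too: opposite shifts of 1.5 SD reduce a within-group correlation of 0.5 to about zero. All shifts, their direction and the median split are assumptions. Only exploratory objective 2 is affected, so the severity is minor.

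**What to change.** In section 6.10, keep the pooled description and add:

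1. A partial rank correlation of SUVmax with thyroglobulin adjusted for group, named as the estimate to interpret for exploratory objective 2. Report it with the within-group correlations and a scatter plot marked by group.
2. A stratified (van Elteren) form of the Mann-Whitney test, with the thyroglobulin cut-point stated.
3. A definition of group: recorded histology or differentiation where available, otherwise the qualifying scan, with a written rule for patients who have both scans. Scan type is only a proxy for differentiation.

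The cost is a few sentences and one degree of freedom, with no extra patients or procedures. The within-group estimates will be imprecise: at n = 20 the 95% interval around r = 0 is tanh(±1.96/√17), about ±0.44. They should be presented as descriptive.

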Signature

Date

Abstract

Title	Gallium-68 Prostate Specific Membrane Antigen (68Ga-PSMA) PET for Imaging of Thyroid Cancer: A Feasibility Study
Patient population	
The study population will consist of patients with thyroid cancer.
 
Key Eligibility Criteria:
 
 • History of thyroid cancer. • Whole body ¹⁸F-FDG PET, I-123 or I-131 scintigraphy within the past 360 days demonstrating uptake • Age 18 years or older at the time of study entry
Rationale for Study	Agents targeting prostate specific membrane antigen (PSMA) are under investigation for both imaging and therapy of prostate cancer. However, despite its name, PSMA expression is not specific to prostate, and is seen in a variety of normal tissues and cancers. In particular, recent case reports have demonstrated that ⁶⁸ Ga-PSMA ligands demonstrate uptake in thyroid cancer. Intriguingly, a recent case report of a patient with thyroid cancer demonstrated a greater sensitivity for metastatic lesions using ⁶⁸ Ga-PSMA as compared to ¹⁸ F-FDG. This suggests the potential use of PSMA PET as a diagnostic (and, in radioiodine-negative thyroid cancers, therapeutic) agent in patients with thyroid cancer.
Primary Objective	
 • To determine the feasibility and utility of ⁶⁸Ga-PSMA PET imaging in patients with thyroid cancer
Secondary Objectives	
 1. To assess the correlation between targeted molecular uptake of ⁶⁸Ga-PSMA-11 in thyroid cancer compared to areas identified as tumor by radioiodine uptake (in well-differentiated cancers) or ¹⁸F-FDG uptake (in poorly differentiated and/or radioiodine-negative cancers). 2. To determine and compare the sensitivity and specificity of ⁶⁸Ga-PSMA-11 PET to ¹⁸F-FDG PET and/or radioiodine scintigraphy
Exploratory Objectives	
 1. To determine if ⁶⁸Ga-PSMA PET uptake is related to tumor differentiation and PSMA staining in tissue pathology when available 2. To determine the correlation between SUV_{max} of target thyroid cancer lesions on ⁶⁸Ga-PSMA PET and serum thyroglobulin levels.
Study Design	This is a single center pilot study investigating the use of ⁶⁸ Ga-PSMA PET in patients with thyroid cancer.
Number of patients	40 patients will be accrued over an approximate 24-month period. It is estimated that all patients will have routine diagnostic imaging, and all patients will have elevated serum thyroglobulin.

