3.2 Number of Subjects

The total sample size is 40 patients enrolled over approximately 24 months.

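### Section 6.10 answers the exploratory correlation questions with Pearson and no stated transformation, leaves the SUV unit unclear, and splits thyroglobulin at an unstated cut; a rank or log-scale analysis with one value per patient would be better at almost no cost

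*Combined protocol and SAP*

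**What the plan says.** Section 6.10 plans three analyses that bear on this point.

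- **Split.** "The patient cohort will be dichotomized by thyroglobulin level", and the per-patient SUVmax-avg "between dichotomized subgroups will be compared using the non-parametric Mann-Whitney U test". No cut is given, and no rule for choosing one.
- **Continuous thyroglobulin.** The relation of SUVmax to "thyroglobulin level as a continuous variable will also be determined using Pearson correlation method".
- **Tissue.** Where archival tissue is adequate, the relation of SUVmax to "tumor PSMA expression will be explored using Pearson correlation method". The scale of expression is not described.

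These serve the thyroglobulin objective and the staining part of the first objective in Section 2.3, headed "Exploratory Objectives, Other Assessments". Section 6.7 records an SUVmax for each lesion, limits analysis to the five largest lesions per study, and allows averaging to SUVmax-avg where needed. The schedule in Section 5.1.4 lists thyroglobulin once, at screening. The Abstract (number of patients) estimates that "all patients will have elevated serum thyroglobulin".

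**The concern.** Three features of the wording weaken the answer to the exploratory questions.

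1. Pearson without a transformation measures a straight-line relation on the measured scale. If a serum marker spans a wide range, its few largest values carry most of the weight. The plan uses a rank test for the split but not for the continuous analysis.
2. The correlation names SUVmax, while the split names SUVmax-avg. If several lesion values per patient are paired with that patient's one thyroglobulin value, the observations are not independent. A cap of five lesions limits that clustering but does not remove it.
3. The cut is open. The obvious candidate, normal against elevated, is unlikely to work if nearly everyone is elevated, so the cut could end up being chosen with the SUV data in view.

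At stake is whether the thyroglobulin and staining results can be relied on when a later study is planned.

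**Working it through.** **The plan's own figure.** None is given for these analyses. The only sizing statement, in Section 6.8, is "Given a power of 0.87, a significance level of 0.05, and a one-sided test" for the sensitivity comparison with 20 patients per comparator. It reproduces as a one-sample exact binomial test of 0.90 against 0.65: rejecting at 17 or more of 20 gives alpha 0.044 and power 0.867. It says nothing about the correlations.

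**Inputs.** From the documents: n = 40 (Section 3.2), Pearson, Mann-Whitney U, no cut. Assumed, because the documents are silent: log thyroglobulin and log SUV are bivariate normal with correlation 0.4; SD of log SUV is 0.6; SD of log thyroglobulin, s, is 0.5 to 2.5; there is one value per patient; tests are two-sided at 0.05.

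**Step 1: why skew costs power.** Under these assumptions the correlation on the measured scale is

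r = [exp(0.4 × s × 0.6) − 1] / √{[exp(s²) − 1][exp(0.6²) − 1]}.

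At s = 1: (1.271 − 1) / √(1.718 × 0.433) = 0.271 / 0.863 = 0.31. At s = 2: (1.616 − 1) / √(53.60 × 0.433) = 0.616 / 4.82 = 0.13. The log-scale value of 0.4 is diluted. In samples of 40 the average r falls less far (0.34 and 0.27), but it also varies more.

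**Step 2: power by simulation, n = 40.**

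| Analysis | Power |
|---|---|
| Pearson on logs | 0.74 to 0.75 |
| Spearman | 0.69 |
| Untransformed Pearson, s = 0.5 | about 0.64 |
| Untransformed Pearson, s = 1 / 1.5 / 2 / 2.5 | 0.54 / 0.45 / 0.39 / 0.35 |
| Mann-Whitney at the median cut | 0.50 |

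As a check on the first row, the Fisher approximation gives atanh(0.4) × √37 − 1.96 = 0.4236 × 6.083 − 1.96 = 0.617, so power is Φ(0.617) = 0.73.

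**Step 3: type I error of the correlation, one value per patient.** With no association, untransformed Pearson rejects in about 0.05 of datasets at every s. It is nonetheless sensitive to single patients. Dropping the patient with the highest thyroglobulin moves r by more than 0.1 in 29% (s = 1) to 44% (s = 2.5) of datasets, against under 0.1% for Spearman.

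**Step 4: free cut.** With no association, taking the best Mann-Whitney result over all cuts from the 20th to the 80th percentile rejects in about 0.27 of datasets. A cut fixed at the median rejects in about 0.05. Neither figure depends on skew, because the test uses ranks.

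**Step 5: lesions treated as independent.** With m lesions per patient and within-patient correlation ρ, the variance of the estimate is inflated by 1 + (m − 1)ρ. Type I error is then about 2 × [1 − Φ(1.96 / √(1 + (m − 1)ρ))].

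| m | ρ | Inflation | Approximation | Simulated |
|---|---|---|---|---|
| 3 | 0.2 | 1.4 | 0.10 | 0.09 |
| 3 | 0.5 | 2.0 | 0.17 | 0.17 |
| 5 | 0.2 | 1.8 | 0.14 | 0.14 |
| 5 | 0.5 | 3.0 | 0.26 | 0.26 |

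Both m and ρ are assumed, with 40 patients. One SUVmax-avg per patient removes the problem.

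**The case against.** The strongest reply is that these analyses are labelled exploratory. Section 6.8 sizes the trial on sensitivity alone, and the one forward-looking criterion in Section 6.10 concerns lesion counts. That stands, and it limits the priority.

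The power loss also rests on an assumed skew. At log SD 0.5 the gap to Spearman is only about 0.05. If the data were close to normal as measured, Pearson would be slightly the better of the two. That also stands: the size of the loss is conditional.

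A reader might go further in several ways that the documents do not support:

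- **That the plan prescribes the raw scale.** It states no transformation, but untransformed analysis is inferred from silence. Section 6.7 also mentions adjusted SUVmax data without defining the adjustment.
- **That one extreme patient will produce false positives.** With one value per patient, the type I error of Pearson stays near 0.05. The sensitivity to one patient concerns the size of r under skew, and it does not apply to the rank-based split.
- **That a normal/elevated split would leave an empty group.** The Abstract only estimates that all will be elevated, and Section 3.3.1 has no thyroglobulin criterion, so some non-elevated patients could enrol.
- **That the split discards the continuous information.** It is run alongside the continuous analysis.
- **That lesion-level analysis is planned.** Section 6.7 offers a per-patient average and the split uses it; the correlation sentence simply does not say which is meant.
- **That the staining result suffers a known loss.** Neither its scale nor its sample size is stated, so no figure can be attached.

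**Conclusion.** The point holds as an improvement to exploratory analyses. The stated method is weaker than an equally simple alternative if thyroglobulin is right-skewed: power of 0.54 to 0.35 for log SD 1 to 2.5, against 0.69 for Spearman, at 40 patients and a log-scale correlation of 0.4. With mild skew the loss is small.

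Two gaps in wording could inflate type I error. One is a cut chosen with the data in view; its 0.27 is a worst case that assumes a full search. The other is lesion values paired with a per-patient marker, giving about 0.09 to 0.26 for 3 to 5 lesions and within-patient correlation 0.2 to 0.5. Neither is certain to occur, but the plan rules out neither.

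The primary objective and the sample size of 40 are untouched. Priority is low to moderate.

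**What to change.** Amend Section 6.10 as follows.

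- For thyroglobulin, use Spearman correlation, or Pearson on log thyroglobulin and log SUV, reported with a 95% confidence interval. Use one SUVmax-avg per patient, and make this the main analysis of the objective.
- For PSMA expression, use Spearman, particularly if expression is scored on an ordinal scale, and state the scale.
- Drop the thyroglobulin split. Alternatively, keep it only as a descriptive display at the cohort median, with that rule fixed before SUV data are seen. A median split used as a test would keep the lower power (0.50), so it should not carry the inference.

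The cost is a wording change. It needs no extra patients, scans or laboratory tests.
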